7.10.2. Vital Signs

The observed values and the change from baseline for vital signs (body temperature, pulse rate, respiratory rate, and supine blood pressure) will be summarized by visit and treatment group.

The number and percent of subjects meeting the following criteria will be summarized considering all post-baseline visits including unscheduled:

- Absolute value of Systolic blood pressure (SBP) < 90 mm Hg
- Absolute value of Diastolic blood pressure (DBP) < 50 mm Hg
- Pulse rate <50 bpm
- Pulse rate > 120 bpm
- Maximum increase from baseline in SBP \geq 30 mm Hg
- Maximum increase from baseline in DBP \geq 20 mm Hg
- Maximum decrease from baseline in SBP \geq 30 mm Hg
- Maximum decrease from baseline in DBP \geq 20 mm Hg.

Clinically significant shifts for blood pressure from baseline to each post baseline visit will be summarized in the following criteria:

Table 7: Blood Pressure Category

Systolic (mm Hg)		Diastolic (mm Hg)	Blood Pressure Category
>180	Or	>120	Crisis
\geq 140	Or	\geq 90	Hypertension Stage 2
130-139	Or	80-89	Hypertension Stage 1
120-129	And	<80	Elevated
<90	Or	<60	Hypotension
<120	And	<80	Normal

7.10.3. Physical Examinations

Physical examination (abdominal, cardiovascular, neurological, respiratory, skin, and general, etc.) results will be summarized by visits and by treatment group.

7.10.4. Electrocardiograms

The following quantitative ECG measurements will be taken during the study:

- heart rate (bpm)
- PR interval (msec)
- Complex in ECG representing ventricular depolarization (QRS) interval (msec)
- Fridericia corrected QT (QTcF) interval (msec)

Descriptive summaries and changes from baseline will be presented by treatment group for the quantitative ECG measurements listed above and the qualitative overall ECG interpretation (categorized as normal; abnormal, insignificant; and abnormal, significant).

Shift tables will present changes from baseline in ECG interpretation (categorized as normal; abnormal, not clinically significant; and abnormal, clinically significant) to each post-baseline visit.

QTcF outliers (value >450 msec or change from baseline >30 msec) will be summarized and flagged in listing.

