Fibroscan VCTE and CAP	X ^f					X			X	X			f. Fibroscan should ideally be performed prior to MRI-PDFF. At Screening, a historical Fibroscan assessment performed within the last 3 months prior to screening may be acceptable.
12-lead ECG (single) ^g	X	B		X		X			X	X	X		g. ECGs will be recorded as single bedside measurements. Additional ECG may be conducted if clinically indicated. ECG should be performed prior to vital signs and laboratory assessments. All ECG data should be provided within 72 hours to the central reader for assessment.
Urine drug screen	X ^h												h. Urine drug screen will be done locally with a standardized kit during screening period by Day 1. If cannot be performed during screening, test can be performed on Day 1, but must be completed before randomization procedures start. Refer to Appendix 2 (Section 10.2).

Assessments	Screening Period ¹	Treatment Period										FU Period	Notes:
		Main Study					Extension Study						
Study Day		1 ²											
Study Weeks	-12 to 0		4 ³	8 ⁴	12 ³	16 ⁴	24 ³	26 ⁵	30 ⁴	38 ³	48 ³	ET ^{3,6}	51 ⁷ /EOS
Visit window (days)			±2	±7	±7	±7	+7	+7	±7	±14	+14		±14
Hematology, and coagulation factors	X	B	X	X	X	X	X	X	X	X	X	X	Refer to Appendix 2 (Section 10.2) for laboratory parameters.
Biochemistry	X ⁱ	B	X	X	X	X	X	X	X	X	X	X	Refer to Appendix 2 (Section 10.2) for laboratory parameters. i. For all subjects, ALT and AST will be collected twice during the Screening period at least 2 weeks apart between the 1 st and 2 nd assessment. A 3 rd assessment, if required, will be collected via unscheduled visit, and performed at least 1 week apart from the 2 nd assessment (refer to Exclusion criterion in Section 5.2.).
FSH	X												Only if required to confirm menopausal status in women under the age of 45 who have amenorrhea >12 months and are not using hormonal contraception or hormone replacement therapy.
LH, FSH, Estradiol		X				X			X				Only for WOCBP who are not on hormonal contraception.
Urinalysis	X	B	X	X	X	X	X	X	X	X	X	X	
HbA1c	X	B		X	X	X		X	X	X	X	X	
HOMA-IR	X	B		X	X	X		X	X	X	X	X	
IGF-1		B		X	X	X		X	X	X	X	X	
Serology	X												Refer to Appendix 2 (Section 10.2) for laboratory parameters (HBsAg, HCV and HIV 1 and 2 antibodies [HCV RNA reflex for HCV Ab+ only]).
Thyroid panel (TSH, FT4, TT3)	X			X	X	X		X	X	X	X	X	

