5.1. Inclusion Criteria

Subjects are eligible to be included in the study only if all of the following criteria apply:

Age and Gender

1. Subjects must be 21 to 75 years of age inclusive, at the time of signing the informed consent form (ICF).
2. Male or female.

Type of Subject and Disease Characteristics

3. Biopsy-confirmed NASH with fibrosis stage F2, or F3 per NASH CRN system and NAS ≥ 4 , with a score of at least 1 in each of steatosis, ballooning degeneration, and lobular inflammation, either through a historical biopsy or a biopsy at screening. A historical biopsy should be obtained within 6 months prior to first day of Screening (i.e., day ICF is signed) that is deemed suitable for interpretation by a central reader if the subject had no significant change in metabolic status (control of diabetes, hyperlipidemia or $>5\%$ weight loss or gain).

Pregnancy and Contraception

Contraceptive use by men or women should be consistent with local regulations regarding the methods of contraception for those participating in clinical studies. Refer to Appendix 4 (Section 10.4) for definitions of women of childbearing potential (WOCBP) and contraception guidance.

4. All subjects (male or female) who are of childbearing potential must agree to use highly effective, double contraception (both male and female partners) during the study. Use of a condom with spermicide in a male subject who underwent vasectomy is also acceptable as double contraception. Use of highly effective, double contraception must continue for 30 days after the last dose of IP. Female subjects should not donate oocytes during this time. Male subjects must not donate sperm during this time. Rhythm methods are not considered as highly effective methods of birth control. Subject abstinence for the duration of the study and 30 days after the last dose of IP is acceptable if it is the subject's regular practice.
5. Females of childbearing potential must have a negative serum pregnancy test at Screening and a negative urine pregnancy test on Day 1. Females of childbearing

potential must agree to undergo a pregnancy test prior to dosing at the timepoints specified in the SoA.

6. Sexually active male subjects whose female partner is pregnant must agree to use a condom.

Informed Consent and Study Requirements

7. Capable of giving signed informed consent, which includes compliance with the requirements and restrictions listed in the ICF and in this protocol.

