Abnormal	$> 40\%$ increase from Assessment 1	$\leq 40\%$ increase from Assessment 1	Eligible
		$> 40\%$ increase from Assessment 1	Excluded

Normal is defined as \leq ULN; abnormal is defined as $>$ ULN (upper limit of normal).

Note: Clinical judgment should be used for subjects with isolated AST increases in whom there is suggestion of another cause of AST increase (e.g., muscle injury as evident by concurrent creatine phosphokinase elevation).

- 19. ECG abnormality by central reader that may, in the opinion of the Investigator, interfere with study participation. Resting QTcF interval of ≥ 450 msec for males or ≥ 470 msec for females (by central reader).
- 20. BMI at Screening < 25.0 or $> 50.0 \text{ kg/m}^2$.

Prior/Concomitant Therapy

- 21. Subject report of use of medications historically associated with secondary NAFLD for more than 2 consecutive weeks in the 12 months prior to screening (e.g., amiodarone, methotrexate, systemic glucocorticoids, tetracyclines, tamoxifen, estrogens or anabolic steroids at doses greater than those used for hormone replacement, valproic acid, and other medications with known hepatotoxicity). Inhaled corticosteroids are allowed.
- 22. Any prior exposure to a FGF21 analog (e.g., including but not limited to pegozafermin, LY2405319, LY3025876, BMS986036, BMS986171, PF05231023, PF-06645849, AKR-001) or FGFR1 activating product, if known.

23. Any investigational drug small molecule (new chemical entity) within 30 days and large molecule (biologics) within 90 days, or 5 half-lives, whichever is longer, prior to Day 1, if known.
24. Subjects taking vitamin E (> 400 IU/day) must be on a stable dose for at least 6 months prior to screening.

Prior/Concurrent Clinical Study Experience

25. Currently participating in or have participated in a study of an investigational agent or has used an investigational device within 30 days prior to the first dose of IP. Note: study participants will not be allowed to participate in other interventional trials for FGF21 analog (e.g., including but not limited to pegozafermin, LY2405319, LY3025876, BMS986036, BMS986171, PF05231023, PF-06645849, AKR 001) or FGFR1 activating products, during the immunogenicity follow up period.

Other Exclusions

26. Inability to undergo a liver biopsy safely for any reason.
27. Subject who cannot undergo MRI for any reason (e.g., contraindication, claustrophobia not controlled by anxiolytic, excessive weight or body size for MRI machine).

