5. DEFINITIONS

5.1. Baseline Definition

For efficacy, safety (except ALT, AST, lipids, and vital signs), and biomarkers each subject's baseline value for that measurement will be defined as the last non-missing value collected on or before the day of first study drug dose, or randomization date + 5 days if subjects have never been dosed. Other baseline values, such as demographics and pertinent medical history etc., is defined as last available value before randomization date.

The definition of baseline of lipid panel labs is the average of last non-missing screening fasting values and Study Day 1 value (Pre-dose, fasting).

The definition of baseline vital signs is the average of the last non-missing screening values and Study Day 1 value (Pre-dose). If there is Case Report Form (CRF) average value on duplicate measurements of BP and/or Pulse on Study Day 1, only the individual values will be included in the baseline derivation.

Baseline ALT and AST were defined as below:

Table 3: Baseline Definition for ALT and AST Values

ALT/AST Screening Assessments			Day 1 ALT/AST Assessment	Baseline Value
Assessment 1	Assessment 2	Assessment 3 (if applicable)		
Normal	Normal	Not applicable	Any	Average of Assessment 1, Assessment 2 and Day 1 (3 tests)
Normal	Abnormal and ≤40% increase from Assessment 1	Not applicable	Any	Average of Assessment 1, Assessment 2 and Day 1 (3 tests)
Normal	Abnormal and >40% increase from Assessment 1	Normal or ≤40% increase from Assessment 1	Any	Average of Assessment 1, Assessment 2, Assessment 3 and Day 1 (4 tests)
		Abnormal and >40% increase from Assessment 1	Not applicable, subject excluded	Not applicable, subject excluded
Abnormal	≤40% increase from Assessment 1	Not applicable	Any	Average of Assessment 1, Assessment 2 and Day 1 (3 tests)
Abnormal	>40% increase from Assessment 1	≤40% increase from Assessment 1	Any	Average of Assessment 1, Assessment 2, Assessment 3 and Day 1 (4 tests)
		>40% increase from Assessment 1	Not applicable, subject excluded	Not applicable, subject excluded

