7. STATISTICAL METHODS OF ANALYSES

7.1. General Considerations

The primary analysis will include data up to the min of (28 days after the last dose date before the completion of all Week 24 assessments, the date all Week 24 assessments completed, Main Study cut-off date).

At final analysis, safety summaries including extent of exposure will report data from both Main Study and Extension Study, based on safety analysis set.

Continuous variables will be summarized by number of patients, mean, standard deviation (SD)/ standard error (SE), median, minimum, and maximum values. Minimum and maximum will be presented to the same number of decimal places as reported/collected. One additional decimal place will be presented for mean and median. Two additional decimal places will be presented for SD/ SE up to a max of three decimal places.

Categorical variables will be summarized by number and percentage of patients. Percentage will be presented to one decimal place. The number of missing values will be presented as a separate category with no percentage, but only if 1 or more patients are missing data for the summary. Otherwise, all categories will be presented (even if no patients are counted in the category). Counts of zero in any category will be presented without percentage.

For analysis purpose, placebo QW and placebo Q2W will be pooled except for exposure summaries and pre-specified supportive analyses.

All statistical tests will be 2-sided and tested at a statistically significant level of 0.05 without adjustment for multiplicity. Confidence intervals will be 2-sided 95%, unless stated otherwise. Two-sided p-values will be presented with four decimal places and values less than 0.0001 will be presented as <.0001.

Both reported units (CN) and standard units (SI) will be presented in listings. Only CN units will be used for tables and figures, unless otherwise specified. Insulin will be presented with conventional unit of μ IU/mL.

All applicable analyses for the primary analysis of the Main Study will be presented as:

<Description>	Placebo Pooled	Pegozafermin 15 mg QW	Pegozafermin 30 mg QW	Pegozafermin 44 mg Q2W
---------------	-------------------	--------------------------	--------------------------	---------------------------

A total column will be presented for the disposition, demography, protocol deviation, medical history, prior/concomitant medication/procedure, and other subject information summaries.

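### The >450 msec limb of the QTcF outlier rule is neither sex-specific nor treatment-emergent, so a woman admitted with a QTcF of 451–469 msec can be counted as an outlier with no change on treatment

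*SAP*

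**What the plan says.** **The outlier rule.** SAP 7.10.4 states: "QTcF outliers (value >450 msec or change from baseline >30 msec) will be summarized and flagged in listing". It gives one level for both sexes, does not say that only post-baseline values count, and sets no condition on the baseline value.

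**The entry limit.** The protocol admits both sexes (inclusion criterion 2: "Male or female"). Exclusion criterion 19 removes subjects with "Resting QTcF interval of ≥ 450 msec for males or ≥ 470 msec for females (by central reader").

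**Baseline and measurement.** SAP 5.1 takes baseline as the "last non-missing value collected on or before the day of first study drug dose". Its exceptions are ALT, AST, lipids and vital signs, so ECG follows the general rule. The protocol's Schedule of Activities says "ECGs will be recorded as single bedside measurements".

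**What else is planned.** SAP 7.10.4 also says "Descriptive summaries and changes from baseline will be presented by treatment group for the quantitative ECG measurements listed above", and QTcF is on that list. It adds "Shift tables will present changes from baseline in ECG interpretation", in normal and abnormal categories rather than QTcF bands. On the control, SAP 7.1 says "For analysis purpose, placebo QW and placebo Q2W will be pooled except for exposure summaries and pre-specified supportive analyses".

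**A comparison within the SAP.** The vital-sign criteria in 7.10.2 are counted over post-baseline visits, unscheduled ones included. Absolute limits and changes from baseline are separate items there.

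**The concern.** The same flag does not mean the same thing in the two sexes. A man had to be below 450 msec to enter, so a later value above 450 msec is a crossing of his entry limit. A woman may have been above 450 msec when she was admitted, and for her the flag may only restate where she started.

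No planned table separates new values above 450 msec from values already there before dosing. The shift tables cover the ECG interpretation, not the QTcF level. If the two limbs form a single count, a woman above 450 msec at baseline is likely to be in it whatever happens, and a real rise of more than 30 msec in her leaves the count unchanged.

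At stake is how readable a descriptive safety table is. Part of the outlier rate in each arm would reflect how many women with a long baseline QTcF were allocated to it, and chance imbalance matters most in the smallest arm.

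**Working it through.** The plan states no figure for this rule, so there is nothing to reproduce. The check has three steps.

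**1. Overlap of the two rules (whole msec)**

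| | Eligible | Flagged by level | Both |
|---|---|---|---|
| Men | below 450 | above 450 | none |
| Women | below 470 | above 450 | 451–469 |

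**2. Share of eligible women already above 450 msec**

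The documents give no QTcF mean or SD. Assume that women's QTcF is normal with mean 410–430 msec and SD 15–20 msec, cut off at the entry limit. Then

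share = [P(X > 450) − P(X > 470)] / P(X < 470).

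- Lowest case (mean 410, SD 15): (0.0038 − 0.0000) / 1.0000 = 0.4%.
- Highest case (mean 430, SD 20): (0.1587 − 0.0228) / 0.9772 = 13.9%. The simulation below gives 14.0%.

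Turning this into a number of subjects would also need the proportion of women, which the documents do not give.

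**3. What the rule does with and without a drug effect**

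Simulation for women, 400,000 draws per case: one post-baseline reading equals baseline plus a shift of 0, 10 or 20 msec plus noise with SD 10 msec (also an assumption). All entries are percentages of all eligible women. The last column applies the same two-limb flag but counts only women with baseline ≤450 msec.

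| Mean, SD | Baseline >450 | SAP flag at shift 0 / 10 / 20 | Flag with baseline ≤450 at shift 0 / 10 / 20 |
|---|---|---|---|
| 410, 15 | 0.4 | 1.4 / 6.3 / 23.1 | 1.1 / 5.9 / 22.7 |
| 410, 20 | 2.1 | 3.6 / 10.3 / 28.0 | 2.1 / 8.4 / 25.9 |
| 420, 15 | 2.3 | 4.8 / 14.3 / 34.8 | 3.3 / 12.2 / 32.6 |
| 420, 20 | 6.1 | 8.5 / 19.1 / 38.7 | 4.0 / 13.4 / 32.7 |
| 430, 15 | 8.7 | 13.0 / 29.1 / 52.4 | 6.9 / 20.9 / 43.7 |
| 430, 20 | 14.0 | 16.8 / 31.8 / 52.6 | 6.3 / 18.6 / 38.7 |

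The >30 msec limb alone gives about 0.1%, 2.3% and 15.9% for the three shifts in every row, because it depends only on the change.

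- **Background.** With no drug effect, the restriction lowers the flagged share from 1.4–16.8% to 1.1–6.9%. In the highest case, (16.8 − 6.3) / 14.0 = 75% of women already above 450 msec are flagged at a single visit with no effect at all.
- **Contrast.** For a 10 msec shift in that case, the ratio to background is 31.8 / 16.8 = 1.9 under the SAP rule and 18.6 / 6.3 = 3.0 under the restricted count. In the lowest case it is 6.3 / 1.4 = 4.5 against 5.9 / 1.1 = 5.4. The dilution is in relative terms. The absolute difference does not shrink: in the highest case it is 31.8 − 16.8 = 15.0 points against 18.6 − 6.3 = 12.3.
- **Small arm.** One subject is 1/16 = 6.3% of the planned 15 mg QW arm, or 1/20 = 5% at the cap of about 20 in SAP 3.3. One subject is 1/64 = 1.6% of pooled placebo.

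The simulation treats the observed baseline as the subject's true level. With single tracings some high baselines will fall back, so the figures illustrate the mechanism and do not predict the table.

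**The case against.** **The two rules do not conflict.** A reader might infer a contradiction. One rule is an eligibility limit and the other a reporting flag, and both can be applied exactly as written. No stopping or success rule depends on the flag. This stands: the rules are unaligned, not contradictory.

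**The signal is not hidden.** A reader might infer that a drug effect would be masked. The documents do not support that. QTcF change from baseline is summarised by arm, the >30 msec limb is tied to each subject's own baseline, and pooled placebo stands beside each dose. Randomisation is expected to spread long baselines over all arms. In every simulated case the combined flag still rises clearly with the shift. This stands.

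**Being admitted at 451–469 msec does not fix the baseline.** Baseline is the last value up to the day of first dose, from a single tracing, so a woman admitted at 455 msec may have a baseline of 445. SAP 6.2 generally uses visits from randomization, so screening tracings would not normally be counted. This stands, and it limits the point to women whose baseline itself is above 450 msec.

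**The limbs may already be separate.** SAP Section 1 places the table shells in other documents, and the sentence in 7.10.4 does not say that the two criteria share a row. This is fair, so the remark about a single count is conditional.

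**Shifts are covered elsewhere.** The safety endpoint in SAP 4.1.5 concerns incidence and shifts of clinically significant ECG findings, which the interpretation shift tables address. The QTcF flag is supplementary. That lowers the importance of the point, but those tables still do not show which values above 450 msec are new.

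**Conclusion.** The point holds as a minor matter of safety reporting. The level limb of the QTcF rule has no sex-specific limit and no treatment-emergent condition, while the protocol admits women up to 469 msec. A woman with a baseline of 451–469 msec can be counted as an outlier without any change.

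The effect is background noise and a weaker relative contrast in one descriptive table, most visible in the 15 mg QW arm. Its size is unknown. The range of about 0.4–14% of eligible women rests wholly on the assumed normal distributions, and the flagging rates also rest on the assumed within-subject SD of 10 msec.

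Neither a contradiction between protocol and SAP nor a masked drug effect follows from the documents. The primary analysis, power and alpha are not touched.

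**What to change.** In SAP 7.10.4, replace the outlier sentence with the following:

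- Number and percentage of subjects with any post-baseline QTcF >450 msec, unscheduled visits included, in two rows: baseline ≤450 msec and baseline >450 msec, each with its own denominator.
- The same rows by sex.
- Change from baseline >30 msec as a separate row.

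This follows the pattern already used for vital signs in SAP 7.10.2. The listing flag can stay as it is.

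Keep 450 msec as the tabulated level for both sexes. Raising it to 470 msec for women would lose some new crossings: a woman going from 430 to 458 msec (+28) is flagged by the present rule but would not be flagged then. Splitting by baseline status solves the problem without that loss, and it also handles a man whose pre-dose tracing on Day 1 happens to exceed 450 msec.

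The cost is one SAP sentence and a table shell. Sex, baseline and ECG values are already collected.

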7.10.5. Bone Mineral Density

Descriptive summaries of absolute value, change and percent change from baseline at each post-baseline assessment in BMD will be presented by treatment group using DXA results.

7.10.6. Immunogenicity

The number and percentage of subjects who develop anti-pegozafermin antibodies will be summarized at each visit by treatment group and pooled pegozafermin group. For those with a positive assessment, the ADA titers will also be summarized. The number and percentage of ADA positive samples with binding specificity (PEG domain specificity and FGF21 domain specificity) and neutralizing immunogenicity will also be summarized. Additional summary tables may be requested.

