9.4.2. Safety Analyses

All safety analyses will be performed on the Safety Analysis Set. Safety assessments will be based on AEs, laboratory values, concomitant medication use, ECG, and vital signs data. Summaries will be presented by treatment group.

Treatment duration and IP received will be summarized by treatment group. Subject incidence of TEAEs will be tabulated by Medical Dictionary for Regulatory Activities (MedDRA) system organ class, MedDRA preferred term, and treatment group. All AEs that started within the first dose of IP and the last dose of the IP+28 days or continuing AEs that worsen the grade post IP will be considered as TEAEs. For subjects who withdraw consent from the study, the end date of the TEAE reporting period will be the earlier of the withdrawal consent date and the date of the last dose of the IP + 28 days. All TEAEs, all treatment-related TEAEs, all treatment-emergent SAEs, and all treatment-emergent serious related AEs will be summarized.

The number (%) of subjects who fail to complete the study and the reason for discontinuation, and the number (%) of subjects who fail to complete the study due to related TEAEs will be summarized and listed.

Safety laboratory tests, concomitant medication use, vital signs, and ECG measures will be summarized by visits and by treatment group.

Results of immunogenicity assessment will be provided by ADA response (number and percent of positive ADA subjects) and immunogenicity profile (e.g., antibody titers, binding specificity), when appropriate.

The effect of ADA on serum pegozafermin concentrations may be evaluated.

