4.1.5. Safety Endpoints

- Frequency and severity of TEAEs and SAEs
- Number of subjects who discontinued due to TEAEs and due to related TEAEs
- Incidence and shifts of clinically significant physical examination findings, ECG data and laboratory abnormalities; safety laboratory evaluations include hematology, blood biochemistry and urinalysis, serum, salivary, and urinary cortisol as appropriate
- Change from baseline in
 - Insulin-like growth factor 1 (IGF-1)
 - Bone biomarkers: Carboxy-terminal collagen crosslinks (CTX), N-terminal propeptide of type 1 collagen (P1NP) and osteocalcin
 - Thyroid stimulating hormone (TSH)
- Absolute and % change from baseline in lumbar spine, total hip, and femoral neck bone mineral density (BMD) as assessed by dual X-ray absorptiometry (DXA)
- Incidence and characteristics of anti-drug antibodies (ADA) and neutralizing antibody (NAb) after dosing (e.g., titer and binding specificity, to the FGF21 and polyethylene glycol [PEG] part of pegozafermin)
- Impact of the presence of ADAs on serum pegozafermin concentrations and clinical safety

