4.2.3. Safety Endpoints

- Number of subjects who discontinued due to TEAEs and due to related TEAEs
- Incidence and shifts of clinically significant physical examination findings, ECG data and laboratory abnormalities; safety laboratory evaluations include hematology, blood biochemistry and urinalysis, serum, salivary, and urinary cortisol as appropriate
- Insulin-like growth factor 1 (IGF-1)
- Bone biomarkers: Carboxy-terminal collagen crosslinks (CTX), N-terminal propeptide of type 1 collagen (P1NP) and osteocalcin
- Thyroid stimulating hormone (TSH)
- Absolute and % change from baseline in lumbar spine, total hip, and femoral neck bone mineral density (BMD) as assessed by dual X-ray absorptiometry (DXA)
- Incidence and characteristics of anti-drug antibodies (ADA) and neutralizing antibody (NAb) after dosing (e.g., titer and binding specificity, to the FGF21 and polyethylene glycol [PEG] part of pegozafermin)
- Impact of the presence of ADAs on serum pegozafermin concentrations and clinical safety
- Levels of endogenous FGF21 at the immunogenicity follow-up visit(s) compared to baseline in NAb positive subjects

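### SAP 7.10.6 counts neutralizing antibodies and domain specificity per ADA-positive sample, so NAb incidence has no subject-level estimate, and ADA is tabulated only by visit

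*SAP*

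**What the plan says.** SAP 4.1.5 lists as a Main Study safety endpoint "Incidence and characteristics of anti-drug antibodies (ADA) and neutralizing antibody (NAb) after dosing". SAP 4.2.3 repeats it for the Extension Study and adds endogenous FGF21 at the follow-up visits "compared to baseline in NAb positive subjects".

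The analysis is in SAP 7.10.6, within the Main Study safety section. It has three parts:

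- **ADA:** "The number and percentage of subjects who develop anti-pegozafermin antibodies will be summarized at each visit by treatment group and pooled pegozafermin group". Titers are summarized for positives.
- **Domain specificity and NAb:** "The number and percentage of ADA positive samples with binding specificity" (PEG or FGF21) "and neutralizing immunogenicity will also be summarized". One sentence covers both, so NAb also takes the ADA-positive sample as its unit.
- **Anything further:** "Additional summary tables may be requested".

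Protocol 9.4.2 is less specific: "Results of immunogenicity assessment will be provided by ADA response (number and percent of positive ADA subjects"), plus an immunogenicity profile. The opening of Protocol Section 9 gives the SAP precedence where the SAP specifies an analysis. SAP 7.12.3 says the complete immunogenicity data, including the follow-up period, will be analyzed separately, and gives no method. SAP 5.1 has a general baseline rule for safety measurements (last value on or before the day of first study drug dose) but does not link it to ADA status.

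**The concern.** Incidence is a proportion of subjects. A proportion of ADA-positive samples answers a different question: given a positive sample, how often does it neutralize? A subject with persistent antibodies can supply several samples and a subject with a transient response only one. In addition, subjects who never become ADA positive drop out of the denominator. A reader who wants the share of treated subjects with neutralizing antibodies will not find it in the specified output.

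For ADA the unit is right but the time frame is incomplete. If the by-visit row means positive at that visit, transient responders at different visits are never added up. If predose positives are not separated, the row mixes pre-existing with treatment-emergent antibodies.

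Immunogenicity is a named safety objective in both parts, and the post-treatment follow-up period was added to study it. The headline immunogenicity rates from this trial should therefore not depend on choices made after the data are seen.

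**Working it through.** The documents state no immunogenicity rate, power or sample size, so there is no figure to reproduce. The check sets the endpoint against the analysis and then shows, on assumed data, how far the planned summaries can sit from incidence.

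**1. Endpoint against analysis**

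| Component | Endpoint (SAP 4.1.5, 4.2.3) | SAP 7.10.6 | Subject-level incidence specified? |
|---|---|---|---|
| ADA | Incidence after dosing | Subjects, at each visit | Only by visit; no any-time line, no baseline rule |
| NAb | Incidence after dosing | ADA-positive samples | No |
| PEG/FGF21 specificity | Characteristic of ADA | ADA-positive samples | No |

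**2. NAb: samples against subjects**

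Input from the documents: 64 subjects planned on 30 mg QW (Protocol 4.1). Assumed: 40 ADA-positive samples, of which 8 are NAb positive.

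- Planned summary: 8/40 = 20.0% of ADA-positive samples.
- If the 8 samples come from 2 subjects: 2/64 = 3.1% of subjects.
- If they come from 8 subjects: 8/64 = 12.5% of subjects.

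The ambiguity survives a by-visit reading. Spread the same counts evenly over four visits: 40/4 = 10 ADA-positive and 8/4 = 2 NAb-positive samples per visit. Each visit shows 2/10 = 20%. The two NAb positives may be the same 2 subjects every time (3.1%) or 2 different subjects each time (4 × 2 = 8, 12.5%).

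**3. ADA: by visit against any time**

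Assumed: four post-baseline visits; 40% of baseline-negative subjects become positive, with onset equally likely at each visit; after onset, each later visit is positive independently with probability *r*.

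With no baseline positives, the proportion positive at visit *v* is 0.40 × (1/4) × [1 + *r*(*v* − 1)].

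- *r* = 0.3: 10%, 13%, 16%, 19% at visits 1 to 4. Ever positive: 40%.
- *r* = 0.9: 10%, 19%, 28%, 37%. Ever positive: 40%.

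A simulation of the same set-up agrees (18.9% and 36.8% at the last visit; 39.5% and 39.8% ever positive).

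If *develop* is read cumulatively instead, the row would be 10%, 20%, 30%, 40%, and its last entry would be the any-time figure. The SAP does not say which is meant.

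**4. Baseline positives**

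Assumed: 10% positive before dosing and at every later visit; other assumptions as above.

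- Ever positive after baseline: 0.10 + 0.90 × 0.40 = 46%.
- Treatment-emergent: 0.90 × 0.40 = 36% of all subjects.

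The 10-point gap depends entirely on how the predose sample is used.

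**5. Switchers**

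Placebo QW subjects re-randomized to 30 mg start active drug at Week 26 (SAP 3.2). The general baseline in SAP 5.1 is tied to first study drug, which for them was placebo, about 26 weeks before any pegozafermin. No immunogenicity baseline is stated for this group.

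**The case against.** Several points on the other side are fair.

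- **ADA is subject-level.** A reader might infer that the plan does not estimate ADA incidence at all. It does not go that far: SAP 7.10.6 counts subjects who develop antibodies, a word that implies new positivity, and Protocol 9.4.2 plans the number and percent of ADA-positive subjects with no by-visit limit. The ADA gap is one of definition.
- **Baseline is not ignored.** A reader might also infer that the predose sample goes unused. The documents do not show this. The sample is scheduled, and SAP 5.1 gives a general safety baseline whose exceptions do not include ADA. What is missing is a stated rule.
- **SAP 4.2.3 is not blocked.** Choosing NAb-positive subjects for the FGF21 comparison uses individual assay results and does not need a summary table.
- **Repeat counting depends on the reading.** If the sample sentence is also by visit, SAP 6.2 generally leaves one assessment per subject per visit, and nobody is counted twice within a visit. This stands, but step 2 shows that any-time NAb incidence still cannot be recovered, and the printed denominator is still ADA-positive samples.
- **Low inferential stakes.** These are descriptive summaries; no test or stated decision rule depends on them. Table shells are separate documents (SAP 1) and may hold more. However, an option to request further tables is not a prespecified estimate, and neither Protocol 9.4.2 nor SAP 7.12.3 gives a subject-level NAb rule.

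**Conclusion.** The point holds for NAb and domain specificity. Followed as written, SAP 7.10.6 yields no share of treated subjects with neutralizing antibodies, although NAb incidence is part of a named endpoint in both study parts. For ADA, the claim is narrower: incidence is counted in subjects but only by visit, with no any-time post-baseline summary and no stated rule for predose positives or for switchers.

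The size cannot be stated from the documents. The illustrations (3.1% or 12.5% behind the same 20%; 19% at the last visit against 40% ever positive; 46% against 36% with baseline positives) rest on assumed counts, onset and persistence. They show that the planned percentages do not determine incidence; they do not predict this trial's results. No efficacy conclusion is affected.

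**What to change.** In SAP 7.10.6, and for the complete-data analysis mentioned in SAP 7.12.3:

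1. Make the main table subject-level. The denominator is pegozafermin-treated subjects with at least one post-baseline sample; the numerator is those ADA positive at any post-baseline time. Give it for the Main Study, to Week 48, and to the end of immunogenicity follow-up.
2. Show baseline ADA status, and count baseline-negative to post-baseline-positive as treatment-emergent. For subjects moving from placebo to 30 mg QW, take baseline as the last sample before the first active dose.
3. Report NAb, anti-FGF21 and anti-PEG on the same subject denominator, with one positive post-baseline result sufficient unless another rule is stated.
4. Keep the by-visit ADA table and the sample-level table as supportive, and say whether the former is positive at that visit or cumulative.

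A titer-rise criterion for boosted responses in baseline-positive subjects is optional; neither document requires one.

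The cost is SAP wording and derived variables from data already collected. The sponsor should confirm that the pre-switch samples of the re-randomized subjects are assayed.
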